- Maximum blood pressure reading of 166/100 mmHg
- Vital pulp (Cold and EPT positive)

Exclusion Criteria:

- History of inadequately controlled hypertension or active thyroid disease
- Five or more nosebleeds in the past month
- Known allergy to oxymetazoline, tetracaine, benzylalcohol or para-aminobenzoic acid
- History of congenital or idiopathic methemoglobinemia
- Taking monoamine oxidase inhibitors, tricyclic antidepressants (e.g. amitriptyline), or non-selective beta adrenergic antagonists (e.g. propranolol)
- Taking oxymetazoline-containing products (i.e., Afrin) in the last 24 hours

- Pregnant and lactating women
- Non vital pulp (Cold and EPT negative)

Study Characteristics:

Design:

Randomized, open label clinical trial

Non-inferiority threshold and Sample size calculation:

The anesthetic efficiency of articaine has been reported in the literature to be around 78 – 88% (Evans et al.). The non-inferiority threshold is the maximum allowable excess of outcome events arising from the novel treatment compared with the standard treatment. The threshold for this study has been selected based on draft guidance set by the FDA (Temple et al.) and was set at 25%. Using nQuery Advisor v7.0, we verified that a sample size of 38 subjects per group would be needed to show a non-inferiority of <25% (one sided alpha of 0.05 and a power of 83%).

Accordingly, each of our study arms will have 90 subjects: 45 in Kovanaze and 45 in Articaine groups.

Accounting for screen failures and dropouts, we will recruit 100 participants in each population totaling 300 for the entire study.

Intervention:

Metered Kovanaze sprays (0.2 ml each spray, St. Renatus) in the nostril on the same side as the tooth of interest. The dose involves:

2 sprays in adult and kids weighing 40 kg or more

1 spray in kids > 6 years but weighing between > 20 kg and < 40 kg

Control:

- Children: 1.0 ml of 4% articaine (containing 1:100000 epinephrine) delivered in the periapex of the tooth of interest by labial/buccal infiltration
- Adults: 1.8ml of 4% articaine (containing 1:100000 epinephrine) delivered in the periapex of the tooth of interest by labial/buccal infiltration

Population:

Our study will evaluate the effectiveness of Kovanaze in three different populations.

Population 1: *Children (aged 6-17 years and weighing >20 kg) requiring specific procedures for treatment of oral disease*

Location: Department of Pediatric Dentistry, 3rd floor, Wood Building

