The biostatistician on the study team ([name]) will generate random sequence using a computer. The randomization will be in block of varying size (4 or 6) and the list will be provided to the following lead faculty who will serve as co-investigators as listed below:

Population 1: Pediatric Dentistry, [name]

Population 2: Endodontics, [name]

Population 3: General Practice, [name]

b. Allocation Concealment:

All random assignments will be placed in sequentially numbered opaque envelopes and will be handled by a staff in the respective department (not a part of the study team). If the participant is found to be eligible for the study, the resident/ student will inform the patient about the study. The team will answer all questions regarding the study and will request consent to participate in the study. After obtaining written patient consent, the department staff (not a member of the study team) will reveal the allocation.

Outcomes:

Patient important outcomes are considered including the primary outcome of completion of intended procedure without rescue anesthetic. This dichotomous outcome (success or failure of anesthesia) is linked to patients' rating of pain on a validated Heft-Parker visual analog scale. The emoji scale will be used for children. Group comparison between the articaine and Kovanaze formulations for anesthetic success will be analyzed by using Fisher's exact test.

Secondary outcomes include objective assessment of hard tissue and soft tissue anesthesia, anxiety scale (STAI-Y6 short form for children and MDAS scale for adults).

[figure not shown]
Adult participants who receive Kovanaze will also be asked to complete a survey to assess the impact of Kovanaze on patient confidence in seeking dental care.

Primary Outcome Measure in Adults:

Proportion of study participants in whom intended dental procedure could be successfully completed without the need for rescue anesthetic.

Heft Parker Scale: Each patient will rate his or her initial pain on a Heft Parker visual analogue scale, a 170-mm line with various descriptive terms. The subjects will be asked to place a mark on the scale where it best described their pain level both at the start and any time during the procedure. To interpret the data, the VAS is divided into the following four categories:

- a. No pain corresponded to 0 mm on the scale.

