Proportion of study participants in whom intended dental procedure could be successfully completed without the need for rescue anesthetic. We will use a 7 point pictorial emoji scale for children. [6] Each patient will rate his or her initial pain on this pictorial scale and will be asked to place a mark on the scale where it best described their pain level both at the start and any time during the procedure. A cut off point of 4 will be chosen to consider anesthetic failure (anything less than 4 will be interpreted as painful).

Secondary Outcome Measures in Children:

1. Onset of meaningful anesthesia:

Patient will be given a stopwatch and will be instructed to press the watch at two different time points:

- a. Onset of anesthesia (T-1 in min): Press the watch when they first perceive pain relief after the administration of local anesthetic
- b. Significant pain relief (T-2 in min): Press the watch the second time when the patient report significant pain relief (>4 in Emoji scale)

At each time of the stopwatch/ timer, the patient will record their pain in VAS scale. Treatment will proceed as long as the Emoji rating is below 4. i.e. no to mild pain. If the pain is moderate to high at any point of the procedure (score >4), the event would be considered anesthetic failure and a rescue anesthetic administered.

2. Spread of anesthesia:

The teeth and the soft tissues on the side of the mouth ipsilateral to the tooth of interest will be evaluated for spread of anesthesia. The number of teeth that are anesthetized will be counted after cold and electronic pulp tests and recorded (maximum possible score is 5). Similarly, the buccal and lingual gingiva will be tested for anesthesia 1 cm below the gingival margin for each of the 5 teeth ipsilateral to the tooth of interest (maximum score of 5). The hard tissue and soft tissue scores will be compared between two groups.

3. Anxiety and Behavior Score in Children:

Two validated questionnaires will be used in children to assess their anxiety and behavior.

a. STAI-Y6 short form Questionnaire:

Participants will be requested to fill in the short form of the State-Trait Anxiety Inventory questionnaire (STAI: Y6 item) before and after the dental appointment. (Marteau et al.)

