2. Mild, soft verbal protest or (quiet) crying as a signal of discomfort, but does not obstruct progress. Appropriate behavior for procedure, i.e., slight start of injection, "ow" during drilling if hurting, etc.
3. Protest more prominent. Both crying and hand signals. May move head around making it hard to administer treatment. Protest more distracting and troublesome. However, child still complies with request to cooperate.
4. Protest presents real problem to dentist. Complies with demands reluctantly, requiring extra effort by dentist. Body movement.
5. Protest disrupts procedure, requires that all of the dentist's attention be directed toward the child's behavior. Compliance eventually achieved after considerable effort by dentist, but without much actual physical restraint. (May require holding child's hands or the like to start). More prominent body movement.
6. General protest, no compliance or cooperation. Physical restraint is required.

Flow of research related procedures on study visit in children:

Screening of EHR will be done to identify potential study participants on a routine clinical visit. During the study visit the study related procedures would be performed in the following order:

1. Go over the study details, answer participant questions and obtain informed consent
2. Administer STAI-Y6 questionnaire
3. Ask patient to rate pain (if present) in the Emoji Scale
4. Reveal allocation (Kovanaze or Articaine)
5. Take baseline BP and heart rate
6. Administer local anesthetic
7. Wait for patient to signal achievement of meaningful anesthesia (using stop watch)
8. Map the extent of soft tissue and hard tissue anesthesia in data collection form
9. Proceed with the intended procedure
10. Assign anesthetic **failure** if subject perceives pain after start of procedure. Record the failure in data collection form and proceed with rescue anesthetic to complete the procedure
11. Assign anesthetic **success** if local anesthesia was adequate to complete the intended procedure without need for rescue anesthetic. Record in data collection form
12. Record patient anxiety and behavior using Venham scale
13. Take end of appointment BP and heart rate

References:

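### The children's emoji cut-off of 4 runs in opposite directions within the same section, so the score that defines failure and triggers rescue in Population 1 contradicts itself.

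*Combined protocol and SAP*

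**What the plan says.** The child endpoint has its own section, which opens as follows: "Proportion of study participants in whom intended dental procedure could be successfully completed without the need for rescue anesthetic. We will use a 7 point". The instrument is an emoji scale, and the text does not say which end of it is worst pain. The cut-off of 4 then appears in four places:

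- Primary Outcome Measure in Children: "anything less than 4 will be interpreted as painful".
- Secondary Outcome Measures in Children, item 1, time point T-2: the child is to "report significant pain relief (>4 in Emoji scale").
- Same item, rule for continuing: "Treatment will proceed as long as the Emoji rating is below 4. i.e. no to mild pain".
- Same item, rescue rule: "If the pain is moderate to high at any point of the procedure (score >4") the event is an anesthetic failure and rescue is given.

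The Outcomes section ties the endpoint to the rating: "This dichotomous outcome (success or failure of anesthesia) is linked to" the patient's pain score. In the children's visit flow, step 10 assigns failure "if subject perceives pain after start of procedure", with no score attached. On numbers, the sample-size section says "each of our study arms will have 90 subjects: 45 in Kovanaze and 45 in Articaine groups"; the context shows that this means 90 per population.

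**The concern.** The first two statements treat a high score as good; the last two treat a high score as bad. They cannot all be followed. The rating decides whether rescue is given, and rescue is the primary failure event, so the conflict reaches the primary endpoint of one of the three populations. It also governs when a child in pain receives more anesthetic. The trial is open label, so anyone who settles the rule case by case does so knowing the allocation.

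If the conflict causes misclassification at the same rate in both arms, a true difference shrinks towards zero. In a non-inferiority comparison, that makes it easier to declare an inferior treatment non-inferior.

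**Working it through.** **1. The four statements side by side.** Number the ratings 1 to 7 (an assumption; the text says only that there are seven points).

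| Rating | Primary-outcome sentence | T-2 | Continue/rescue rules |
|---|---|---|---|
| 1, 2, 3 | painful (failure) | not relief | continue |
| 4 | not painful | not relief | neither continue nor failure |
| 5, 6, 7 | not painful | relief | failure, rescue |

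The primary-outcome sentence and the continue/rescue rules give opposite answers for 6 of the 7 ratings. A rating of 4 is not painful under the first, blocks treatment under the continue rule, and is not a failure under the rescue rule. T-2 relief (5 to 7) covers exactly the scores that the rescue rule calls failure, and no score satisfies both T-2 and the rule for continuing.

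**2. Comparison with the adult text.** Under Secondary Outcome Measures in Adults, item 1, relief and continuing both sit below 54 mm and failure at or above it, so the direction is consistent. The child item closely follows the same wording and still asks for a VAS rating. Its T-2 inequality has been turned round, while the continue and rescue inequalities have not. That looks like an incomplete adaptation.

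**3. The plan's sample size.** Inputs from the sample-size section: margin 25 points, one-sided alpha 0.05, power 83%. The success rate used is not stated. Assuming 78% in both arms, the low end of the 78–88% quoted:

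n = (z₀.₉₅ + z₀.₈₃)² × 2p(1−p) / δ² = (1.645 + 0.954)² × 2 × 0.78 × 0.22 / 0.25² = 37.1, rounded up to 38 per group.

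This reproduces the stated 38. The emoji cut-off does not enter the formula, so sample size is unaffected.

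**4. What misclassification could do.** The documents give no misclassification rate, so m below is an assumption shown over a range. If a fraction m of successes and the same fraction of failures are miscoded in each arm, observed success is q = p(1−m) + (1−p)m, and the observed difference is (1−2m) times the true one.

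Take articaine at 83% (middle of 78–88%) and Kovanaze at 58%, so the true difference is at the margin, with 45 per arm. Non-inferiority is declared if the one-sided 5% Wald lower bound for Kovanaze minus articaine exceeds −25 points. The Wald bound is an assumption, because the plan names only Fisher's exact test. Exact binomial enumeration gives:

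| m | Articaine observed | Kovanaze observed | Difference (points) | Chance of wrongly declaring non-inferiority |
|---|---|---|---|---|
| 0 | 83.0% | 58.0% | −25.0 | 5.1% |
| 5% | 79.7% | 57.2% | −22.5 | 8.4% |
| 10% | 76.4% | 56.4% | −20.0 | 12.7% |
| 20% | 69.8% | 54.8% | −15.0 | 24.8% |

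With articaine at 78% or 88% and the same 25-point deficit, m = 10% gives 11.9% or 13.5%. A score test at 83% gives 5.3, 8.9, 13.5 and 25.7% for the four values of m.

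**5. One-way errors.** If only successes are miscoded, q = p(1−m); if only failures are, q = p + (1−p)m. In both cases the difference shrinks by (1−m) rather than (1−2m). For m = 5, 10 and 20%, the false non-inferiority rate is 6.4, 7.7 and about 12% for successes only, and 6.7, 8.7 and 14.5% for failures only.

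**6. If the drugs are truly equal.** At 83% in both arms, two-way error of 10% lowers observed success to 76.4% in each arm and cuts the chance of showing non-inferiority from 93.5% to 87.6%.

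**The case against.** The strongest reply is that the endpoint is rescue itself, not a score recoded afterwards. Each of the four statements pairs its number with words, and the words agree: painful, relief, no to mild pain, moderate to high pain. Step 10 speaks of perceived pain. To code a child wrongly, a clinician would have to follow the digit against both the words and the child. This stands, and it makes wholesale reversal unlikely. A child whose ratings fall on both sides of 4 during the procedure would also fail under either reading.

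The error model is open to challenge too. No value of m has support in the documents. One-way error roughly halves the 24.8% figure. If a clinic simply adopts one direction, the error is all or none. Equal rates in both arms are not assured in an open-label trial, and unequal rates could bias either way. If the drugs are equal, misclassification works against Kovanaze. All of this stands, so the error rates are illustrative only.

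A figure is missing from the available Outcomes text and may show the scale's anchors. It could settle the direction but could not reconcile four inequalities that point two ways. Step 10 may be shorthand for the scored rule, since the adult flow uses the same wording. It carries no score, however, and read literally it counts mild pain, which the onset item allows.

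None of these points removes the contradiction.

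**Conclusion.** The concern holds. The current text gives a self-contradictory threshold for the primary failure event in the 90 planned children (45 per arm), and two of the four numeric statements are wrong whichever direction was intended. The documents do not show which two. This is a drafting error in a decision rule; the design, margin and sample size are untouched.

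The practical size is uncertain. The verbal labels and step 10 should keep misclassification low, but the plan gives no rate. Over an assumed 5 to 20% per arm, with the true difference at the margin and articaine at 83%, the false non-inferiority rate would be roughly 6 to 15% under one-way error and 8 to 25% under two-way error, against a nominal 5%. Those figures rest on equal error in both arms and a Wald bound. The need for correction does not depend on them: a primary-endpoint rule that cannot be applied as written must be fixed.

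**What to change.** - State in the text which end of the 7-point scale is worst pain.
- Use one direction and one inequality in all four places, and say explicitly whether a score of 4 is success or failure.
- Align step 10 of the children's visit flow with that rule, so that mild pain is treated the same way in both.
- Record the raw emoji rating on the data-collection form, so that each success or failure can be checked against it.
- Replace the leftover reference to the VAS in the children's onset item with the emoji scale (minor).

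The direction and cut-off are for the investigators to choose. The cost is protocol wording and a form change, with no extra patients or visits and no change to the sample size.
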